**8.5 Expedited Reporting**

The Sponsor will report all relevant information about suspected unexpected serious adverse reactions that are fatal or life-threatening as soon as possible to the Food and Drug Administration (FDA), applicable competent authorities in all the Member States concerned, and to the Central Ethics Committee, and in any case no later than 7 days after knowledge by the Sponsor of such a case, and that relevant follow-up information will subsequently be communicated within an additional 8 days.

Given that all-cause mortality is the primary efficacy endpoint in the study, all death cases will not be automatically unblinded by the case processing team. Death cases, where there is a plausible cause of death that is related to study drug administration, will be treated as potential suspected unexpected serious adverse reactions and processed as such and reported as needed. The DSMB

will periodically monitor deaths in aggregate, analyzed by treatment group, as detailed in the DSMB charter.

All other suspected unexpected serious adverse reactions will be reported to the FDA, applicable competent authorities concerned, and to the Central Ethics Committee concerned as soon as possible but within a maximum of 15 days of first knowledge by the Sponsor.

The Sponsor will also inform all Investigators as required.

## **8.6 Clinical Laboratory Evaluations**

Standard clinical laboratory profiles for chemistry will be evaluated at Screening, Day 1, Day 3, Day 5, Day 7, the EOT Visit, the TOC Visit, the LFU Visit, and the ET Visit. Serum creatinine will be evaluated daily while the patient is receiving study drug and will be analyzed at the local laboratory to assess the need for dose adjustments. All Screening laboratories will be performed at the local laboratory and may have been collected as standard of care within 48 hours prior to randomization, with the exception of serum creatinine determination, which must be obtained at the local laboratory within 24 hours before the first dose of study drug. All other samples are to be sent to the central laboratory. The Day 5 safety chemistry panel will be performed at the local laboratory and sent to the central laboratory.

Standard clinical laboratory profiles for hematology including complete blood count (with red blood cell count, total white blood cell count with differential counts, platelet count, hemoglobin, and hematocrit) will be performed at Screening, Day 1, Day 3, Day 5, Day 7, the EOT Visit, the TOC Visit, the LFU Visit, and the ET Visit.

A urinalysis including urine dipstick analysis for leukocytes, nitrites, or a catalase test of the urine specimen, microscopic evaluation, specific gravity, and pH will be performed at Screening, Day 1, Day 3, Day 5, Day 7, the EOT Visit, the TOC Visit, the LFU Visit, and the ET Visit.

A highly sensitive urine or serum pregnancy test will be performed at Screening, the EOT Visit, and the ET Visit for women of childbearing potential.

See [Appendix B](#) for a list of central clinical laboratory analytes.

Standard of care safety laboratory profiles should also be performed by the local laboratory. Abnormal values of laboratory parameters must be followed up to normalization or stabilization at the discretion of the Investigator.

In China all sites will perform all laboratory tests at the local laboratory, following the timepoints outlined above.

## **8.7 Vital Signs**

Vital signs (including systolic and diastolic blood pressure, heart rate, respiratory rate, and, for ventilated patients, oxygen therapy and respiratory settings including FiO2 and PEEP) will be taken after at least 5 minutes in a seated or supine position. Vital signs will be recorded at Screening, all days that the patient receives study drug treatment, the EOT Visit, the TOC Visit, the LFU Visit, and the ET Visit. Vital signs should be collected at the same time as assessments of signs and symptoms.

## 8.8 Medical/Surgical History Assessments

Medical and surgical history will be obtained and evaluated at Screening to confirm the patient's eligibility to enroll in the study.

## 8.9 Electrocardiograms

Twelve-lead ECGs will be performed for all patients at Screening, at the end of the first infusion of study drug on Day 1, at EOT, and at the ET Visit. If clinically indicated, the 12-lead ECGs will be repeated as close as possible following the end of the infusion of study drug on the day on which the post-dose PK samples are drawn (Day 4 [ $\pm 1$  day]; day selected at the discretion of the Investigator). All 12-lead ECGs will be performed after the end of the infusion and after the patient has been in a supine position for at least 10 minutes. The value at Screening will be used for assessing the QTcF exclusion criterion. All 12-lead ECGs will be performed and read locally. The following ECG parameters will be recorded:

- Heart rate;
- QRS interval;
- PR interval;
- RR interval;
- QT interval; and
- QTc interval.

All ECGs will be evaluated for the presence of abnormalities by a qualified local physician. The ECGs will be classified as 1 of the following:

- Normal;
- Having a not clinically significant abnormality; or
- Having a clinically significant abnormality.

An example of a clinically significant abnormality may be a corrected QTcF  $\geq 480$  msec.

## 8.10 Physical Examinations

A complete physical examination will be performed at Screening, Day 3, Day 5, Day 7, at the EOT Visit, and at the ET Visit. A limited physical examination will be performed, if needed, at Day 2, Day 4, Day 6, Day 8 to Day 14 (if EOT has not already occurred), at the TOC Visit, and at the LFU Visit.

A complete physical examination must include source documentation of weight, skin, head and neck, heart, lung, abdomen, extremities, back/flank/costovertebral angle tenderness, and neuromuscular assessments. Height will only be collected at Screening. Limited physical examinations are symptom-based. When clinically indicated, a prostate exam can be performed, at the discretion of the Investigator.

Physical examinations may be performed at unscheduled time points if deemed necessary by the Investigator.

### 8.11 Chest X-Ray/Radiology/Ultrasound

Chest X-rays, MRIs, or CT scans will be performed in patients with HABP, VABP, or VP at Screening and the TOC Visit, and as clinically indicated to evaluate for the presence of infiltrates. Ultrasounds may also be performed for patients with HABP, VABP, or VP at Screening. If an ultrasound is performed, a confirmatory X-ray or CT scan should be performed within 24 hours. Imaging should be conducted per institutional guidelines and results recorded in the source documents and the eCRF.

### 8.12 Mechanical Ventilator Assessments

Patients whose primary indication for enrollment into the study is HABP, VABP, or VP and who require mechanical ventilation support will be managed by the study Investigators per institutional guidelines. Data regarding mechanical ventilation settings will be captured in the source documents and the eCRFs.

### 8.13 Safety Monitoring and Assessment of Abnormal Liver Function Tests

Management and discontinuation criteria for abnormal liver function tests (LFTs) have been designed to ensure patient safety and evaluate liver event etiology. Safety monitoring for LFTs will occur from randomization until 30 days following the last administration of study drug; however, any abnormal LFT will be monitored according to the Safety Monitoring Plan. Investigators should evaluate standard of care laboratory reports in addition to study laboratory reports when monitoring for LFTs.

#### Abnormal liver chemistry criteria:

The Investigator or sub-Investigator must review patient laboratory reports to identify if they meet the following criteria:

- Moderate abnormality that happened after study drug administration:
  - AST or ALT  $>2 \times$  baseline or evidence of progressively increasing levels despite improvement of underlying infection; or
  - Total bilirubin  $>2 \times$  baseline or evidence of progressively increasing levels despite improvement of underlying infection.
- Severe abnormality:
  - Confirmed values of AST or ALT  $>3 \times$  ULN **and** total bilirubin  $>2 \times$  ULN or evidence of acute hepatic insufficiency or failure, as evidenced by progression of Child-Pugh score to B or C; or
  - Persistently high values of AST or ALT  $> 5 \times$  ULN for 14 days.

Action to be taken by Investigator:

If any 1 of the abnormal liver chemistry criteria is met, the Investigator or sub-Investigator must do the following:

- Obtain a detailed history of symptoms and prior or concurrent diseases. The Investigator should ensure that the medical history form captures any preexisting illness that may be relevant in assessing hepatic function;
- Obtain a history of concomitant drug use (including over-the-counter/herbal/dietary supplements);
- Obtain a history of exposure to environmental chemical agents;
- Following the initial observed elevation, every effort should be made to have the patient reassessed within 24 hours to 48 hours. Repeat LFTs will be performed and sent to the central laboratory. Liver function tests may also be repeated via the local laboratory at the discretion of the Investigator;
- Patients who have an Investigator-assessed, study drug-related elevation of their LFTs must be monitored 2 to 3 times per week until liver function chemistries (ALT, AST, alkaline phosphatase, and total bilirubin) completely return to normal range or return to the baseline level and associated clinical signs and symptoms return to baseline levels. If the elevation of LFTs is attributed to a non-study drug-related issue (eg, chronic hepatitis, chronic cholestasis, concomitant treatments, cardiovascular causes, etc), the patient should be monitored until the LFTs stabilize or return to the patient's baseline level and associated clinical signs and symptoms return to baseline levels. The Investigator should contact the Medical Monitor to discuss additional management and follow-up of patients with elevation of LFTs;
- The event must be reported to Medpace within 48 hours to 72 hours after its occurrence on a Liver Event Form;
- Consider a consultation with a specialist such as a hepatologist; and
- Consider performing liver imaging (ie, MRI, CT, or ultrasound).

Hy's Law definition:

The definition of Hy's Law is as follows:

1. AST or ALT  $>3 \times$  ULN;
2. Total bilirubin  $>2 \times$  ULN;
3. No evidence of intra- or extra-hepatic bilirubin obstruction (elevated alkaline phosphatase) or Gilbert's Syndrome; and
4. No evidence of any other reason for increase in transaminases as noted above.

**If the first 3 criteria of Hy's Law are met in a concurrent blood sample, the case must be reported as an SAE.**

Criteria for study drug discontinuation (severe hepatic abnormalities):

In the absence of an explanation for increased liver enzymes, the patient should be discontinued from the study drug. Discontinuation should be considered if:

- ALT or AST  $>10 \times$  ULN;
- ALT or AST  $>5 \times$  ULN for more than 2 weeks or progressively increasing transaminases despite clinical improvement of underlying infection;
- AST or ALT  $>3 \times$  ULN and total bilirubin  $>2 \times$  ULN or international normalized ratio  $>1.5$  (for patients who are not on coumadin);
- AST or ALT  $>3 \times$  ULN along with signs or symptoms compatible with hepatitis or hypersensitivity (eg, fatigue, nausea, vomiting, right upper quadrant pain or tenderness, jaundice, fever, rash, or eosinophilia [ $>5\%$ ]); or
- Close monitoring for a patient with moderate hepatic laboratory test abnormality is not possible.

Follow-up examination:

If any abnormal liver chemistry criteria are met, the following assessments should be obtained at the LFU Visit and documented in a Liver Event Form:

- Clinical symptoms course;
- Concomitant medications: over-the-counter/herbal/dietary supplements (start and stop dates);
- Alcohol use;
- Risk factors for non-alcoholic steatohepatitis, such as diabetes, obesity, and hypertriglyceridemia;
- Autoimmune hepatitis/cholangitis;
- Wilson's disease; and
- Laboratory assessments. Based on the patient's history, other testing may be appropriate, including:
  - Acute viral hepatitis (A, B, C, D, E, or other infectious agents); and
  - Other laboratory tests, including international normalized ratio and direct bilirubin.

## 9 STATISTICS

### 9.1 Analysis Populations

This study is designed to estimate treatment efficacy of ABC infections, with a pivotal component in Part A.

The ITT Population will include all patients randomized to study drug treatment (ETX2514SUL plus imipenem/cilastatin or colistin plus imipenem/cilastatin) in Part A or enrolled in Part B, regardless of whether the patient actually receives study drug.

The Modified ITT (MITT) Population will include patients in Parts A and B who meet ITT criteria and receive any amount of study drug. The MITT Population will be considered the Safety Population. Patients with HABP/VABP/VP who were randomized to Part A on the basis of a BPP rapid test result but were subsequently withdrawn due to a lack of a culture growing ABC will be counted in the MITT and Safety Populations.

The m-MITT Population will include patients who meet MITT criteria and have an ABC organism isolated as the qualifying culture specimen, as confirmed by the central and/or local microbiology laboratory. If an isolate for testing at the central laboratory is not available, the local laboratory data can be used to confirm the presence of ABC organism, as long as the local laboratory uses modern methods of diagnosis such as molecular-based tests, matrix-assisted laser desorption/ionization time-of-flight mass spectrometry, Vitek, Phoenix, etc (ie, not conventional biochemical or manual phenotypic methods). Patients with HABP/VABP/VP who are enrolled based upon a positive BPP rapid test for ABC, but subsequently are found to have respiratory sample cultures that do not grow ABC (by the local laboratory), will be withdrawn from the study drug treatment as detailed in [Section 4.3](#). These patients will not be included in the m-MITT Population but will remain in the MITT Population.

The CRABC m-MITT Population will include patients who meet m-MITT criteria and have a baseline ABC organism that is confirmed to be carbapenem-resistant (MIC to imipenem/meropenem  $\geq 8$  mg/L) by the central laboratory or by the local laboratory if the central laboratory is not able to identify the isolate for any reason. Patients will be excluded from the CRABC m-MITT Population if they have isolates that are deemed by the central laboratory to be resistant to ETX2514SUL (MIC  $> 4$  mg/L) or colistin (MIC  $\geq 4$  mg/L), if their blood culture or respiratory samples are collected more than 72 hours prior to randomization, if they are transferred from Part A to Part B, or if they are enrolled with infections other than ABC pneumonia or bloodstream infection (ie, ABC infections other than HABP, VABP, VP, and bacteremia). A sensitivity analysis for the primary efficacy endpoint will be performed for patients whose eligible culture is  $> 48$  hours from the first dose of study drug, as well as for all patients with and without evidence of non-susceptibility to colistin and ETX2514SUL at baseline.

The CE Population will include patients who meet m-MITT criteria and meet evaluability criteria (meet key inclusion criteria, do not have key exclusion criteria, received at least 72 hours of study drug [ie, 12 doses of ETX2514SUL plus 12 doses of imipenem/cilastatin or 6 doses of colistin plus 12 doses of imipenem/cilastatin in patients without dose adjustments] to be a clinical cure, received at least 48 hours of study drug [ie, 8 doses of ETX2514SUL plus 8 doses of imipenem/cilastatin or 4 doses of colistin plus 8 doses of imipenem/cilastatin in patients without dose adjustments] to be a clinical failure, received  $\geq 80\%$  of anticipated doses, and did not have a clinical response of indeterminate at the TOC Visit).

The ME Population will include patients who meet m-MITT criteria and CE criteria and have an appropriately collected culture specimen and interpretable culture result when specimen collection is clinically indicated at the TOC Visit.

The CRABC ME Population will include patients who meet ME criteria and who have a baseline ABC organism that is confirmed to be carbapenem-resistant (and susceptible to ETX2514SUL for Parts A and B and susceptible to colistin for Part A).

The PK Population will include patients who receive any amount of study drug and have evaluable PK data.

## 9.2 Statistical Methods

Continuous variables will be summarized using the number of non-missing observations, arithmetic mean, standard deviation, median, minimum, and maximum values as descriptive statistics. Categorical variables will be summarized by using the frequency count and the percentage of patients in each category as descriptive statistics.

All comparisons in Part A will be for ETX2514SUL plus imipenem/cilastatin versus colistin plus imipenem/cilastatin. The efficacy endpoints for Part B will be summarized descriptively only and will be used to supplement results in Part A. Listings of individual patient data will be produced. A complete analysis of efficacy and safety data will be performed and detailed in the SAP.

### 9.2.1 Patient Population and Characteristics

The number of patients randomized, treated, completed, and discontinued early from the study and the reasons for discontinuation will be summarized descriptively. In addition, reasons leading to study discontinuation will be summarized for each treatment group. The number and percentage of randomized patients included in each analysis population will also be presented.

Summary statistics will be provided by treatment group for demographics (eg, age, gender, race, and ethnicity) and for baseline characteristics.

### 9.2.2 Analysis of Efficacy

#### 9.2.2.1 Primary efficacy analysis

The primary efficacy endpoint for the study is 28-day all-cause mortality in the CRABC m-MITT Population in Part A. Patients in the CRABC m-MITT Population who discontinue study drug prematurely in Part A for any reason will be included in the assessment of 28-day all-cause mortality, provided consent has not been withdrawn.

A sensitivity analysis for the primary efficacy endpoint will be performed for patients whose eligible culture is >48 hours from the first dose of study drug, as well as for all patients with and without evidence of non-susceptibility to colistin and ETX2514SUL at baseline. Details of the sensitivity analysis will be described in the SAP.

The non-inferiority assessment will be based on the 2-sided 95% confidence intervals (CIs) for the difference ( $[\text{ETX2514SUL} + \text{imipenem/cilastatin}] - [\text{colistin} + \text{imipenem/cilastatin}]$ ) in 28-day all-cause mortality rates between the treatment groups. Non-inferiority will be concluded if the upper limit of the 2-sided 95% CI is less than +20%.

If non-inferiority is achieved, a test of superiority will be performed.

The analysis of the primary efficacy endpoint 28-day all-cause mortality will also be performed in the ITT Population.

#### 9.2.2.2 Secondary efficacy analysis

The number and percentage of patients in each response category for the secondary efficacy endpoints will be summarized by treatment group for the populations defined earlier. Two-sided 95% CIs for the difference in outcome rates between the treatment groups in Part A will be provided.

Part B data will be analyzed separately from Part A using descriptive statistics.

Further subgroup analyses will be conducted, and details of the analysis will be described in the SAP.

#### 9.2.2.3 Exploratory efficacy analysis

Exploratory endpoint analysis will be described in the SAP. Exploratory endpoints for health resource utilization difference between treatment groups (such as length of ventilation, intensive care unit stay, hospitalization, additional antibiotic use, etc) will be reported separately. Efficacy analysis for patients with HABP/VABP/VP who are identified as positive for ABC by BPP molecular methodology will be explored.

### 9.2.3 Pharmacokinetic Analysis

Descriptive statistics will be provided for PK concentration data and PK parameters. All PK analyses will be performed using the PK Population.

#### Intense pharmacokinetic group:

Pharmacokinetic samples will be obtained from the first approximately 30 patients randomized in Part A on a schedule detailed in [Section 7.9](#). The PK samples will be collected for both treatment groups in Part A to keep the study data blinded. The PK samples obtained from the ETX2514SUL group will be analyzed for ETX2514 and sulbactam concentrations using a validated assay by a central bioanalytical laboratory. Pharmacokinetic assessment of the initial 15 patients on ETX2514SUL in Part A will be performed by an independent PK assessor, prior to the opening of enrollment in Part B. The independent PK assessor will conduct sequential PK analysis from patients as they are enrolled. An initial aggregate assessment of PK parameters will be done after enrollment of the first 8 HABP/VABP/VP patients randomized to ETX2514SUL. The independent PK assessor will report results to the DSMB, relative to concentrations projected in the population PK model, once data from all 15 patients on ETX2514SUL is available. However, if the preliminary analysis of the first 8 patients with HABP/VABP/VP on ETX2514SUL reveals evidence of inadequate exposure this will be escalated to the DSMB.

#### China Mainland intense pharmacokinetic group:

The intense PK sampling will also be performed on the first approximately 20 patients randomized in Part A from China Mainland sites. The PK samples obtained from patients who have received the ETX2514SUL treatment will be analyzed for ETX2514 and sulbactam concentrations, which will be applied to build the population PK model combined with data from the sparse PK group.

#### Sparse pharmacokinetic group:

All other patients enrolled in the study (Parts A and B) will have a sparse PK sampling, which will be used to better inform the population PK model.

Analysis of the PK data and incorporation into the population PK analysis and PK/PD model will be described in a separate PK Analysis Plan.

#### 9.2.4 Analysis of Safety

All patients who receive any amount of study drug (MITT Population) will be included in the safety analyses. Patients who received the wrong study drug for their entire course of treatment will be analyzed in the group based on the drug received.

A primary analysis of safety will be performed for Part A to assess the proportion of patients with nephrotoxicity, as measured by the RIFLE criteria based on the Safety and CE Populations.

Overall safety will be assessed for Part A and Part B in the Safety Population. The number and percentage of patients in each treatment group reporting at least 1 occurrence of a TEAE for each unique system organ class and preferred term will be tabulated. A TEAE is defined as an adverse event occurring on or after the administration of the first dose of study drug. Treatment-emergent adverse events will also be tabulated by treatment group, severity, and the relationship to study drug as assessed by the Investigator. The number and percentage of patients in each treatment group reporting at least 1 occurrence of a treatment-emergent SAE will be tabulated. The number and percentage of patients (in each treatment group) prematurely discontinuing study drug treatment due to a TEAE will be tabulated by system organ class and preferred term. Adverse events of special interest in Part A will be summarized for all patients by treatment.

Safety laboratory data will be presented by descriptive statistics of the post-baseline value and the change from baseline, as well as the number and percentage of patients with potentially clinically significant laboratory values. Descriptive statistics of vital signs and ECG parameters and the change from baseline will also be presented. An outlier analysis of the ECG parameters will be conducted.

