#### 5.4.1 Unblinded Investigator

An unblinded Investigator at each site will evaluate criteria for clinical outcomes, conduct causality assessment for adverse events, and assess clinical signs and symptoms at study visits for patients in both Part A and Part B. For patients in Part A, a blinded assessor will also evaluate criteria for clinical outcomes, conduct causality assessment for adverse events, and assess clinical signs and symptoms at study visits. The unblinded Investigator must be a qualified physician, able to perform medical evaluations, and determine medical diagnoses (eg, Principal Investigator, sub-Investigator). For consistency, whenever possible, the same unblinded Investigator should complete all unblinded assessments for a study patient. If there is a discrepancy between the assessment of the blinded assessor and unblinded Investigator, the assessment from the blinded assessor will be used. If there is a missing assessment from either the blinded assessor or unblinded Investigator, the other available assessment will be used. An adjudication committee may be organized for endpoint adjudication should it be deemed necessary by the DSMB. In such a case, a charter will be developed that describes their activities.

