### 8.1.3 Assessment of Adverse Events by the Investigator

The unblinded Investigator will assess the severity (intensity) of each adverse event as mild, moderate, or severe. In Part A, in addition to the unblinded Investigator, a blinded assessor will also be responsible for the causality assessment, and as detailed below.

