#### Causality assessment:

The relationship of an adverse event to the administration of the study drug is to be assessed by the blinded assessor and the unblinded Investigator for Part A and by the unblinded Investigator for Part B, according to the following definitions:

No (unrelated, not related, no relation) – The time course between the administration of study drug and the occurrence or worsening of the adverse event rules out a causal relationship and another cause (concomitant drugs, therapies, complications, etc) is suspected.

Yes (related) – The time course between the administration of study drug and the occurrence or worsening of the adverse event is consistent with a causal relationship and no other cause (concomitant drugs, therapies, complications, etc) can be identified.

The definition implies a reasonable possibility of a causal relationship between the event and the study drug. This means that there are facts (evidence) or arguments to suggest a causal relationship.

The following factors should also be considered:

- The temporal sequence from study drug administration-
  - The event should occur after the study drug is given. The length of time from study drug exposure to event should be evaluated in the clinical context of the event.
- Underlying, concomitant, intercurrent diseases-
  - Each report should be evaluated in the context of the natural history and course of the disease being treated and any other disease the patient may have.
- Concomitant drug-
  - The other drugs the patient is taking or the treatment the patient receives should be examined to determine whether any of them might be recognized to cause the event in question.

- Known response pattern for this class of study drug-
  - Clinical and/or preclinical data may indicate whether a particular response is likely to be a class effect.
- Exposure to physical and/or mental stresses-
  - The exposure to stress might induce adverse changes in the recipient and provide a logical and better explanation for the event.
- The pharmacology and PK of the study drug-
  - The known PK properties (absorption, distribution, metabolism, and excretion) of the study drug should be considered.

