#### 8.1.4 Adverse Events of Special Interest

Adverse events of special interest will be analyzed, summarized, and reported in the clinical study report. Statistical comparisons will be made between the investigational and control groups in Part A.

Adverse events of special interest and their definitions include the following:

- Allergic and hypersensitivity reactions: Severe and serious adverse drug reactions from the Medical Dictionary for Regulatory Activities (MedDRA) Standardized MedDRA Queries of allergy and hypersensitivity;
- Nephrotoxicity: Using the RIFLE criteria for the duration of the study (see Table 6), and
- Emergent infections and superinfections: All serious and severe events in the MedDRA system organ class of infections and infestations other than the indication infection (ie, ABC).

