#### 9.4.1. Adverse Events

A treatment-emergent adverse event (TEAE) is defined as an adverse event occurring on or after the administration of the first dose of study drug. An overview of adverse events will be provided which summarizes the incidence of the following categories:

- All AEs,
- All TEAEs,
- Drug-related TEAEs,
- TEAEs by severity,
- SAEs,
- Drug-related SAEs,
- SAE leading to death,
- TEAE leading to discontinuation of study drug, and
- SAE leading to discontinuation of study drug.

Patients with multiple events will be counted only once within each category. Severity grade and relationship will be counted using the maximum severity and the strongest relationship respectively for a patient with multiple TEAEs.

The number and percentage of patients reporting a TEAE in each treatment group will be tabulated by SOC and PT; by SOC, PT, and severity; and by SOC, PT, and relationship (related or unrelated to study drug and imipenem/cilastatin). Summary tables will be presented alphabetically by SOC and decreasing frequency of PT in the EXT2514SUL group within SOC. For all analyses of TEAEs, if the same AE (based on PT) is reported for the same patient more than once, the AE is counted only once for that PT and at the highest severity and strongest relationship to study drug.

The number and percentage of patients reporting a drug-related TEAE, a SAE, a treatment emergent SAE, a drug-related treatment-emergent serious adverse event (TESAE), and a TEAE leading to discontinuation of study drug in each treatment group will be summarized by SOC and PT.

A list of patients who have SAEs, a list of patients who discontinue from study drug, and a list of death will be provided. All adverse events will be listed.

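### The protocol's relatedness tables name the Investigator, who is unblinded in Part A, although Protocol 5.4.1 and SAP 3.3.1 give priority to the blinded assessor's causality rating; SAP 9.4.1 leaves the rater open

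*Protocol*

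**What the plan says.** The protocol's safety analysis text (9.2.4, repeated in the synopsis) tabulates treatment-emergent events by treatment group, severity and "the relationship to study drug as assessed by the Investigator". It does not mention the blinded assessor.

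Protocol 5.4 lists the Principal Investigator among the unblinded staff. Protocol 5.4.1 gives causality to that role in both parts: "An unblinded Investigator at each site will evaluate criteria for clinical outcomes, conduct causality assessment for adverse events". It then adds the second rater: "For patients in Part A, a blinded assessor will also evaluate criteria for clinical outcomes, conduct causality assessment for adverse events". On disagreement between the two, "the assessment from the blinded assessor will be used"; if one rating is missing, the other stands. SAP 3.3.1 repeats this text.

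Protocol 8.1.3 agrees. It says that "a blinded assessor will also be responsible for the causality assessment" in Part A, and its causality paragraph has the relationship "assessed by the blinded assessor and the unblinded Investigator for Part A and by the unblinded Investigator for Part B".

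SAP 9.4.1 plans tables by relationship, and tables of drug-related events, drug-related serious events and drug-related treatment-emergent serious events. It does not say whose rating is used. SAP 9.3.2 contains a disagreement rule, worded for clinical outcome only.

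**The concern.** Part A is assessor-blind because the regimens could not be masked. A second causality rating by someone who does not know the arm is the plan's protection for relatedness, which depends heavily on judgement. The protocol's analysis section names the rater who should yield on disagreement, and the SAP's safety section does not correct it.

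Protocol 1.4 calls colistin's renal and neurological toxicity well described, and Protocol 8.1.3 tells raters to weigh what is known of the drug class. A rater who knows the arm can apply that knowledge arm by arm; a blinded rater cannot. The drug-related tables serve the secondary objective of comparing the safety of the two treatments, so a reader would take an excess of related events on colistin as a finding. If the rater is not fixed in advance, there are also two candidate sets of tables to choose from once results are known.

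**Working it through.** No arithmetic applies: the question is which of two collected ratings feeds the tables. The texts compare as follows.

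| Place | Who rates causality in Part A | Which rating counts |
|---|---|---|
| Protocol 5.4.1 | Both | Blinded on disagreement; the other if one is missing; not limited by type of assessment |
| Protocol 5.4.2 | Blinded assessor, at endpoint visits | Blinded assessor's data go into the eCRF |
| Protocol 8.1.3 | Both | Not stated |
| Protocol 9.2.4 and synopsis | Not stated | The Investigator |
| SAP 3.3.1 | Both | Same general rule as Protocol 5.4.1 |
| SAP 9.3.2 | Not covered | Blinded on disagreement, for clinical outcome |
| SAP 9.4.1 | Not stated | Not stated |

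1. *Within the protocol.* Section 5.4.1 lists clinical outcome, causality, and signs and symptoms, then gives the disagreement rule without restricting it to any of them. Section 9.2.4 names the Investigator for one of those items. On a plain reading, the two give different answers whenever the raters differ on a Part A event.

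2. *Within the SAP.* Section 3.3.1 supports the blinded rating. Section 9.4.1, from which the tables will be programmed, is silent. The one disagreement rule in the SAP's analysis sections does not mention causality. A programmer could follow SAP 3.3.1 or Protocol 9.2.4, with different results.

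3. *Outputs that depend on the answer.* These are the tables by relationship and the drug-related event, serious event and treatment-emergent serious event tables. The allergic event of special interest may also depend on it. Its definition is "Severe and serious adverse drug reactions from the Medical Dictionary for Regulatory Activities (MedDRA) Standardized MedDRA Queries of allergy and hypersensitivity", and Protocol 8.1.1 defines an adverse drug reaction by causal relationship without naming a rater.

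4. *Outputs that do not.* The primary efficacy endpoint is all-cause mortality. The RIFLE comparison uses creatinine and GFR. The overall adverse event, serious event and discontinuation tables count events regardless of relatedness.

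5. *Size.* The documents give neither a rate of related events nor a rate of disagreement between raters, so no figure for the bias can be derived.

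**The case against.** The best reply is that the plan already contains the right rule. SAP 3.3.1 puts the blinded rating first immediately after listing causality. Protocol 9.2 leaves the full safety analysis to the SAP, and SAP 9.4.1 drops the reference to the Investigator. The word may also be generic in Protocol 9.2.4: section 8.1.3 has the Investigator in its title yet assigns causality to the blinded assessor too, and the sentence in 9.2.4 has to cover Part B, where only the Investigator rates. This stands as far as it goes. It rules out the stronger reading that the SAP has adopted the open-label rating. It does not remove the explicit wording in Protocol 9.2.4 or fill the gap in SAP 9.4.1.

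A second reply is that the disagreement rule was meant for clinical outcome only, since Protocol 3.1 and 7.6 and SAP 5.5.1 and 9.3.2 attach it there. The documents do not settle this. On that view, though, the blinded causality ratings would have no stated use in the analysis, which also needs clarifying.

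Third, the blinded assessor sees limited parts of the chart and rates at endpoint visits, so some events may lack a blinded rating. That is fair, and it is why the Investigator's rating is needed as a fallback and as a supportive analysis.

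A reader might also infer that the SAP's rule on repeated events, under which "the AE is counted only once for that PT and at the highest severity and strongest relationship to study drug", lets an open-label rating of related override a blinded rating of unrelated. The text does not support this. The rule applies when a patient has several events or the same preferred term more than once; it collapses events, not raters.

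**Conclusion.** The inconsistency is real and worth correcting, but narrow. Protocol 9.2.4 and the synopsis conflict with Protocol 5.4.1 and SAP 3.3.1 on whose causality rating counts in Part A, and SAP 9.4.1 does not resolve it. The affected outputs are the drug-related tables and possibly the allergic event of special interest. No primary comparison is touched. For renal toxicity, the plan has an objective measure that needs no causality judgement.

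The conclusion assumes that the Investigator in Protocol 9.2.4 is the unblinded role described in 5.4.1, and that the unrestricted rule in 5.4.1 and SAP 3.3.1 covers causality, as its position in the text suggests. A bias against colistin is plausible, given its known toxicity, but it is inferred. A reader might be tempted to attach a number of percentage points to it; nothing in the documents supports one.

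**What to change.** In Protocol 9.2.4, the synopsis and SAP 9.4.1, state: *In Part A, relationship to study drug is the blinded assessor's rating, with the Investigator's rating used only where the blinded rating is missing (as in Protocol 5.4.1 and SAP 3.3.1). Part B uses the Investigator's rating.* Apply the same rating wherever an adverse drug reaction defines the allergic event of special interest. Show the Investigator-rated Part A tables, and agreement between the raters by arm, as supportive. Expedited reporting is unchanged.

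The cost is a wording change in both documents and one extra set of supportive tables. No new data are needed, because the protocol already requires both ratings. The change should be made before treatment-group results are seen.
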